We propose a pilot clinical trial on the use of perioperative pregabalin in order to decrease ureteral stent related symptoms and decrease opioid usage after ureteroscopy with stent placement. Patients undergoing ureteroscopy with stent placement will receive a single dose of 300 mg pregabalin PO in the preoperative area. We will assess safety and feasibility of studying this regimen at our institution, with the aim of performing a randomized, placebo-controlled, double-blinded study in the future.

OBJECTIVES AND SCIENTIFIC AIMS

Primary Hypothesis

It is safe and feasible to study perioperative pregabalin in ureteroscopy with stent placement at our institution.

Exploratory Hypotheses

We hypothesize that the use of the perioperative pregabalin will:

- decrease ureteral stent related symptoms at 3 days post-op
- decrease the probability of a patient requiring narcotic pain medication
- decrease the total amount of narcotic pain medication used
- decrease the unplanned contact between the patient and the healthcare system related to the stent
- improve patient satisfaction after ureteroscopy with stent placement

Primary Endpoints

The primary endpoints will be as follows:

- Adverse events related to study drug
- Verified correct administration of study drug
- Correct use of study instruments

Secondary Endpoints:

Secondary endpoints include the following:

- Ureteral Stent Related Symptom Questionnaire (USSQ) [1] score at 3 days post op
- Monitored prescribing of narcotic pain medication
- Number of patients taking narcotic pain medication at several time points
- Oral morphine equivalents the patient has used at several time points
- Number of unplanned contacts between the patient and the healthcare system within 30 days
- Score on standardized evaluation of patient satisfaction

BACKGROUND AND STUDY DESIGN/INTERVENTION

The prevalence of urolithiasis is greater than 8% and increasing in the United States (US) [2]. There are several treatment options, including ureteroscopy (with or without laser lithotripsy), extracorporeal shock wave lithotripsy, and percutaneous nephrolithotomy. A recent study in California demonstrated that ureteroscopic treatment was employed in more than 40% of interventions [3], with some nationwide estimates up to 59% [4]. At least 300,000 stone

interventions are performed yearly in the US on working age adults [5], thereby, at least 120,000 ureteroscopies are. There are several other indications for ureteroscopy, including diagnosis of structural anomaly and diagnosis and management of ureteral and renal pelvic tumors.

Depending on the specifics of the procedure, it may be advisable to place a ureteral stent intraoperatively [6]. The most commonly used variety of stent is the double J stent [7], which has long been known to cause post-operative pain in around 80% of patients, as well as irritative symptoms in a sizeable portion [8, 9]. A validated questionnaire (the Ureteral Stent Symptom Questionnaire [USSQ]) exists to evaluate symptoms of ureteral stents and their effects of quality of life [1].

Alpha-blockers decrease ureteral stent discomfort when compared to placebo [10, 11]. Anti-muscarinic medications (specifically tolteridine) have also been shown to be helpful with stent related discomfort independently, or in addition to alpha blockade [12], though the evidence is mixed [13]. A recent systematic review failed to find any studies of other medications for stent related discomfort that met inclusion criteria [14]. Subsequently, a well-designed study demonstrated the utility of mirabegron for indwelling stent symptoms [15].

Recent guidelines recommend the use of multimodal treatment strategies in the management of postoperative pain [16]. In several contexts gabapentin or pregabalin have been shown to be a beneficial part of such a strategy. For example, in percutaneous nephrolithotomy, a randomized, placebo-controlled, double-blind study demonstrated that a single dose of 600mg of oral gabapentin 1 hour before surgery significantly decreased catheter-related bladder discomfort, number of patients requiring opioid pain relief, and amount of opioid pain relief when used [17]. Similarly, outside urology, several well-designed trials demonstrate the positive effects of perioperative pregabalin or gabapentin in the elective, outpatient surgery setting [18-20]. Several reviews and meta analyses have also supported the use of perioperative gabapentin or pregabalin in various settings [21-24]. The principal side effects of pregabalin are temporary cognition/coordination changes, with a very low risk of serious side effects [25]. No well-constructed studies to date have examined the perioperative use of gabapentinoids in post-ureteroscopy ureteral stent related symptoms.

We propose a study to extend the literature base on the use of perioperative pregabalin to ureteroscopy with stent placement through a prospective, randomized controlled trial. In order to ensure safety and feasibility of this future study, we will first perform a small pilot. We will administer study medication and study questionnaires. There will be additional components of study evaluation. This will be used to inform the design of a future trial.

CRITERIA FOR SUBJECT ELIGIBILITY

Subject Population

Undergoing elective ureteroscopy with stent placement by [name] at University of Missouri Hospital and affiliated facilities

Subject Inclusion

Age \geq 18 years

Subject Exclusion

- Renal insufficiency (eGFR $<$ 30 mL/minute/1.73 m²)
- Chronic indwelling ureteral stent
- Chronic opioid use
- History of opioid abuse
- Chronic gabapentinoid use
- Plan for inpatient hospitalization
- Pregnancy
- Inability of the patient to consent for themselves in English
- Allergy to gabapentinoid
- Liver failure or hepatic dysfunction

OVERVIEW OF STUDY DESIGNATION

Design

This is a pilot clinical trial on the use of perioperative pregabalin in order to decrease ureteral stent related symptoms and decrease opioid usage after ureteroscopy with stent placement. Patients undergoing ureteroscopy with stent placement will receive a single dose of 300 mg pregabalin PO in the preoperative area.

Pre-op standardized care

After obtaining written consent, patients will be enrolled. All patients will be told the following by a member of the study staff:

“We will be administering several medications before, during, and after your procedure to help with pain. We expect that you will be able to go home with just non-steroidal pain medication.” They will also be counseled on the risks and benefits of non-steroidal anti-inflammatory drugs (NSAIDS).

Subsequently, all patients will be given a single dose of pregabalin 300 mg PO with a sip of water approximately one hour before surgery. This will be administered per standard institutional practice. It will be recorded in the regular medical chart of the patient.

Post-op standardized care

Perioperative care, surgery and anesthesia, for all subjects will be per standard hospital protocol.

A standardized post-operative regimen will be used, consisting of a single belladonna & opium suppository, a single dose of ketorolac 30mg IV, and ondansetron 4mg IV. A single dose of hydrocodone 5mg with acetaminophen 325mg PO will be available PRN pain.

To qualify for discharge from the PACU, all patients will have had to have met a standardized set of discharge criteria. They will have to have ambulated, voided, tolerated PO intake, and have pain subjectively adequately controlled.

On PACU discharge, patients will be given a prescription for 20 tablets of 50mg diclofenac, 20 tablets of acetaminophen 650mg to be taken on a scheduled basis every 6 hours, and mirabegron 50mg once daily PO to be taken until stent removal [15]. There is no universal standard of care discharge regimen after ureteroscopy, but a similar one to this has been shown to be safe and effective [26]. Patients will receive a standardized sheet of return precautions. They will receive packets of questionnaires to be completed along with pre-addressed and pre-stamped envelopes. They will be instructed to only seek pain medication from the urology team for the next month. Should they have need for further pain medication, patients will be instructed to call the clinic [see supplementary material]. They will be offered their choice of another 3 days of NSAID or oxycodone 5mg q6h PRN pain 6 tablets. Further treatment will be at provider discretion. The clinic staff will be instructed to record these prescriptions.

THERAPEUTIC AND DIAGNOSTIC AGENTS

Pregabalin is an oral agent approved for use in fibromyalgia and neuropathic pain. A single dose of 300mg PO will be given to all patients.

RECRUITMENT PLAN

Patients will be recruited from the practice of [name] in the Division of Urology, Department of Surgery. The study will be introduced to every eligible patient scheduled for ureteroscopy with stent placement by the participating consenting physicians from the Department of Surgery-Urology Division and a written consent obtained prior to surgery by the consenting research personnel. Candidate subjects will be provided time to consider the study, to read the informed consent document at their convenience, and discuss the study with family and others, as desired. It will be clearly indicated that non-enrollment in the study will not negatively affect the patient's care.

PRETREATMENT EVALUATION

This study does not require any additional pretreatment evaluations other than those which are part of current clinical care standards for a patient undergoing ureteroscopy with stent placement at University of Missouri. Preoperative evaluations typically include the following:

- Routine history and physical examination to include documentation of any comorbidities, medications (including complementary and alternative medications), family history, social history (alcohol and tobacco usage), height, body weight
- Past medical history including previous treatment for addiction
- Past surgical history including other uses of stents in the patient's lifetime
- Evaluation of renal function
- Any woman of child bearing age who believes she may be pregnant receives a pregnancy test

SURGICAL PLAN

The technique of surgery will have been determined to be ureteroscopy with stent placement based on the discretion of the surgeon and patient. None of the techniques utilized in the study are considered experimental and all are considered standard therapeutic options for patients with

indications for this procedure. Typical indications include nephroureterolithiasis and evaluation for malignancy.

The operating team will consist of surgeons on faculty at University of Missouri Department of Surgery-Urology Division. The procedures are performed under standardized general anesthesia with standard intraoperative vital sign monitoring.

EVALUATION DURING TREATMENT/INTERVENTION

Not part of usual care

This protocol requires several evaluations outside those typically used. These are all questionnaires.

Timing	Questionnaire	Respondent
Day of surgery	Screening questionnaire	Study staff
	Baseline surgery	Patient
	Post-op surgeon	Treatment staff
	PACU	Patient/PACU nurse
	Aldrete	PACU nurse
	Evaluation of trial	Patient
	Evaluation of trial	PACU nurse
	3 days post op	Early patient questionnaire
	USSQ	Patient
	Evaluation of trial	Patient
7 days post op	Early patient questionnaire	Patient
	Evaluation of trial	Patient
30 days post op	30 days post op study	Study staff
	Late patient questionnaire	Patient
	Evaluation of trial	Patient
	90 days post op	Late patient questionnaire
	Evaluation of trial	Patient
	6 months post op	Late patient questionnaire
	Evaluation of trial	Patient
	1-year post op	Late patient questionnaire
	Evaluation of trial	Patient
	Untimed	Unanticipated contact
	Evaluation of trial	Patient

Usual care

Routine evaluation and management for those undergoing ureteroscopy with stent placement include:

ASA classification, assigned by the anesthesiologist

Deep venous thrombosis prophylaxis per standardized pathway

Estimated blood loss

Use of intraoperative fluids (crystalloid, colloid, blood products)

TOXICITIES/SIDE EFFECTS

Various symptoms have been associated with the administration of pregabalin in the perioperative setting. The risk of serious adverse events in this use of pregabalin is low [25] and the potential benefits of this treatment may outweigh the risks. This will be recorded in the PACU side effect and PACU nursing questionnaires.

Surgical complications will be assessed prospectively and retrospectively and reviewed using the institutional standard for complications reporting for all surgical patients as followed by the Department of Surgery. Standardized graded complications and adverse effects at UM utilize the five-point modified Clavien-Dindo system. Grade I include complications requiring monitoring but no intervention; Grade II requires bedside or medical treatment; Grade III constitute adverse events requiring surgical or procedural intervention with return to normal functioning; Grade IV includes disabling, life-threatening complications with resulting functional loss and grade V is death of the patient. This is a modification of the Clavien-Dindo system for reporting complications with defined, categorized and classified events that will be segregated into time periods of ≤ 30 days, 31-90 days and > 90 days after surgery and includes medication complications following NCI CTCAE version 5 guidelines.

CRITERIA FOR THERAPEUTIC RESPONSE/OUTCOME ASSESSMENT

If the surgery is aborted for any reason before placement of a ureteral stent, the patient will be removed from the study and replaced. Based on past experience these issues are rare events.

The intraoperative period is defined as the period from anesthesia induction to the extubation of the trachea. The surgical time is determined from the incision to the final skin closure.

The postoperative period is defined as the period from the extubation to various study endpoints.

Blood loss is defined as the estimate accounted from the suction device and absorptive sponges during the procedure, as described and agreed upon by the surgeon, anesthesiologist, circulating nurse, and surgical technician as covered by institutional guidelines.

The patient's pain will be evaluated with a visual analogue scale of pain [27]. This may either be done digitally or by paper [28].

A validated questionnaire (the Ureteral Stent Symptom Questionnaire [USSQ]) exists to evaluate symptoms of ureteral stents and their effects of quality of life [1]. This will be used to evaluate how patients tolerate the stents.

Patient satisfaction will be assessed at PACU discharge as part of the patient's PACU discharge questionnaire. Similarly, satisfaction will be evaluated via questionnaires at subsequent time points.

CRITERIA FOR REMOVAL FROM STUDY

Patients will be withdrawn from the study if they express a desire to do so, if it is determined to be in the patient's best interest to do so, or if they do not undergo initiation of their surgical procedure as stipulated previously. For this pilot, if a patient fails to receive the study drug, they will be withdrawn from the study and analysis of this failure will be undertaken.

BIOSTATISTICS

Sample Size

The primary purpose of this study is to evaluate safety and feasibility of studying perioperative pregabalin at our institution, with the aim of performing a randomized, placebo-controlled, double-blinded study in the future. 10 patients will complete the study. This is a number that will allow for evaluation of potential serious side effects and feasibility. This number is also small enough that it will not waste resources or delay the future larger study. We estimate that 20 patients will need to be enrolled so that 10 will complete the study. This number of patients will be enrolled over 3 months.

Analysis

Descriptive statistics will be used in reporting patient outcomes in this pilot study. As there is no control group, significance tests will not be performed. Several questionnaires have narrative components which will be compiled and analyzed in a systematic method.

Proposed Analyses

Pre-specified parameters to be reported include the following:

- Serious adverse events
- All adverse events
- Proportion of enrolled patients completing the study
- Adverse events related to study drug
- Ureteral Stent Related Symptom Questionnaire (USSQ) [1] score at 3 days post op
- Monitored prescribing of narcotic pain medication
- Number of patients taking narcotic pain medication at several time points
- Oral morphine equivalents the patient has used at several time points
- Number of unplanned contacts between the patient and the healthcare system within 30 days
- Score on standardized evaluation of patient satisfaction

RESEARCH PARTICIPANT REGISTRATION AND RANDOMIZATION PROCEDURES

Research Participant Registration

We will confirm eligibility as defined in the section entitled Criteria for Patient/Subject Eligibility.

We will obtain informed consent, by following procedures defined in section entitled Informed Consent Procedures.

DATA MANAGEMENT ISSUES

The research team will be responsible for project compliance, data collection, abstraction and entry, data reporting, IRB correspondence, problem resolution and prioritization and coordination of the protocol study team activities. The data collected for this study will be entered into a secure departmental server or will be stored online in the university approved resource, REDCap [29]. Source documentation and regulatory binders will be stored in a locked filing cabinet within a locked department office space. These sites are exclusively used for research documents and only members of the research team will have access to files for this study.

Quality Assurance

Routine data quality reports will be generated to assess missing data and inconsistencies. Accrual rates, and extent and accuracy of evaluations will be monitored throughout the study period. Potential problems will be brought to the attention of the study team for discussion and action.

Data and Safety Monitoring

The MU Health Care Data and Safety Monitoring Plans can be found online.

There are several different mechanisms by which clinical trials are monitored for data, safety and quality. There are institutional processes in place for quality assurance (e.g., protocol monitoring, compliance and data verification audits, therapeutic response and staff education on clinical research QA) and departmental procedures for quality control, plus institutional committees that are responsible for monitoring the activities of the clinical trials program.

PROTECTION OF HUMAN SUBJECTS

Benefits and Risks

The experimental intervention (perioperative pregabalin administration) is currently used at University of Missouri Hospital through the ERAS protocol. Numerous studies have shown significant patient benefits in all fields, including Urology. Several reviews have demonstrated the efficacy and safety of perioperative gabapentinoid administration. The principal side effects of pregabalin are temporary cognition/coordination changes, with a very low risk of serious side effects. Therefore, we do not believe that the therapeutic aspects of this trial pose any serious risk different from patients undergoing ureteroscopy with stent placement under standard procedures.

Toxicities and side effects

Adverse outcomes are not anticipated with the regimen of pregabalin used in this study. Patients are closely monitored during the perioperative period and any serious events will be immediately brought to the attention of the study staff. All potential side effects will be recorded in questionnaires.

Alternatives / Therapeutic options

The alternative to participation in the trial would be to undergo ureteroscopy with stent placement according to the surgeon's standard practice and not to participate in the study. The

patient may or may not receive pregabalin in this case. No other aspect of patient care would differ.

Financial Costs and Burdens

Subjects will not be compensated for their participation. The cost involved in this study is study medication and administration. As these are potentially part of standard treatment, these will be billed to patients as other hospital charges.

Privacy and Confidentiality

We will keep the study records confidential. No identifiers will be used in any reports or publications resulting from the study.

Volunteering Nature of the Study

Participation is entirely voluntary. All aspects of patient's care and monitoring will be unaffected by whether the patient chooses to consent for the study.

Serious Adverse Event (SAE) Reporting

Any SAE will be reported to the IRB as soon as possible, but no later than 5 calendar days. The reporting procedure will be followed as outlined in the University of Missouri protocol found in the "Core Standard Operating Procedure for Event Reporting."

INFORMED CONSENT PROCEDURES

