STATISTICAL ANALYSIS PLAN

Project Title: Perioperative pregabalin as part of a multimodal treatment plan for pain after

ureteroscopy with stent placement: a pilot

IRB Number: 2013680 Version Number: 1.1 Version Date: 11/20/2019

Principal Investigator: [name]

Funding Source: Departmental Clinical Trial Phase: Not Phased

Clinicaltrials.gov Number: NCT03927781 Study Drug/Study Device: Pregabalin

Principal Investigator	[name]	Department of Surgery Urology
		Division
Co-Investigator	[name]	Department of Surgery Urology Division
Consenting Professional(s)	Donartment of Surgery	DIVISION
Consenting Professional(s)	Department of Surgery-	
Department	Urology	

University of Missouri University Hospital Department of Surgery Urology Division [name] Descriptive statistics (counts, proportions, medians) will be used to describe all data. We will describe the demographic information of the patients enrolled and the number of patients approached to meet full enrollment. We will assess the proportion who anticipated needing opioid pain medication, who appropriately received pregabalin, who received opioid pain medication at discharge, who had emergency room visits or hospitalizations in the first 30 post-operative days, and who received opioid prescriptions within the first 30 post-operative days. We will describe the number of oral morphine equivalents prescribed. We will include median USSQ scores. We will describe proportions reporting possible adverse effects and pain level reported. All analyses will be performed in R version 3.5.1. There will be no statistical tests performed.

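### No result is pre-specified as counting against the primary hypothesis of safe and feasible, proportions are planned without intervals, and the sample-size text overstates what 10 patients show about serious side effects

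*Protocol*

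**What the plan says.** The protocol's Primary Hypothesis is that "It is safe and feasible to study perioperative pregabalin in ureteroscopy with stent placement at our institution". The Primary Endpoints are "Adverse events related to study drug", "Verified correct administration of study drug" and "Correct use of study instruments". None has a threshold, and correct use of instruments is not defined. The end of the Background and Study Design section gives the pilot's role: "In order to ensure safety and feasibility of this future study, we will first perform a small pilot". It adds that the results will feed into the design of the later trial.

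Under Biostatistics, Sample Size, 10 patients are to complete, about 20 are expected to be enrolled to achieve this, and accrual is forecast at 3 months. The justification for 10 is: "This is a number that will allow for evaluation of potential serious side effects and feasibility".

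Under Analysis, "Descriptive statistics will be used in reporting patient outcomes in this pilot study", with no significance tests because there is no control group. The SAP agrees: it lists counts, proportions and medians, and states "There will be no statistical tests performed". Neither document mentions a confidence interval.

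The protocol's Proposed Analyses list includes adverse events and the proportion completing, but neither correct administration nor correct use of instruments. The SAP adds the proportion who appropriately received pregabalin; it too is silent on instruments.

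**The concern.** A pilot whose hypothesis is that something is safe and feasible should let a reader see which findings would weaken that statement, and how firmly the data can support it. Here neither is possible from the plan. No value of any primary endpoint is marked as unfavourable, and the planned summaries carry no measure of uncertainty.

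The safety half is the more exposed. The protocol itself expects a very low risk of serious side effects (Background; Benefits and Risks), yet justifies 10 patients as enough to evaluate them. A report of no serious events in 10 could then be taken as support for safety, although so few patients leave a wide range of true rates open.

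Denominators also matter. Under Criteria for Removal from Study, a patient who does not receive the drug is withdrawn. If correct administration were computed only among those remaining, these failures would drop out of the proportion meant to measure them.

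**Working it through.** **Inputs.** From the protocol's Sample Size section: 10 completers, about 20 enrolled. The documents give no event rate, precision target, alpha or power, so there is no power calculation to reproduce. Serious event rates of 2% and 5% are assumptions, used only to show a range.

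**The plan's own figure.** 20 enrolled for 10 completers implies 50% non-completion: 10 / (1 − 0.5) = 20. The 50% is itself derived from the 20 and the 10, so this shows internal consistency and no more.

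**Upper limit with no events.** The exact (Clopper-Pearson) two-sided 95% upper limit for 0 of n is 1 − 0.025^(1/n).
- n = 10: 1 − 0.025^(1/10) = 30.8%
- n = 20: 1 − 0.025^(1/20) = 16.8%

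One-sided 95% limits, 1 − 0.05^(1/n), are 25.9% and 13.9%. The number dosed is not fixed by the plan. It should lie roughly between the 10 completers and the 20 enrolled, so the two rows bracket the likely case.

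**Chance of seeing no event, (1 − p)^n.**

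| Assumed true rate p | n = 10 | n = 20 |
|---|---|---|
| 2% | 0.98^10 = 82% | 0.98^20 = 67% |
| 5% | 0.95^10 = 60% | 0.95^20 = 36% |

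A clean record in 10 patients is thus the more likely outcome at either assumed rate.

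**Feasibility proportions.**
- 10 of 10 correctly dosed: exact lower limit 0.025^(1/10) = 69.2%.
- 10 of 20 completing, exactly as forecast: exact 95% interval 27.2% to 72.8%.

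**Could the forecast serve as a pass mark?** Suppose the rule were at least 10 of 20 completing. At a true completion rate of 50%, P(X = 10) = 184,756 / 1,048,576 = 0.176. By symmetry P(X ≥ 10) = 0.5 + 0.176/2 = 0.588. A pilot performing exactly as forecast would miss the mark 1 − 0.588 = 41% of the time. The forecast is an expected value, not a minimum acceptable value.

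**The case against.** Descriptive reporting suits an uncontrolled pilot of 10, and the absence of significance tests is not a fault. That stands: nothing here calls for a test or a larger sample.

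A reader might infer that any result would be taken as support for the randomized trial. The documents do not say so. They say the pilot will inform the design of a later trial, which allows for modification. What can be said is narrower: no result is named in advance as counting against the hypothesis.

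A reader might also infer that very low and very high completion out of 20 could equally be called feasible. The protocol fixes the number of completers at 10 and only estimates the 20, so a shortfall would appear mainly as extra enrolment or time. No limit is set on either, but the contrast in completers is not one the plan produces.

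The plan also contains real checks. Failures to give the drug are to be analysed; accrual and the extent and accuracy of evaluations are monitored (Quality Assurance); serious adverse events go to the IRB within 5 calendar days. The SAP reports the number approached. None of these says what would weaken the hypothesis. The institutional monitoring plan is cited but not included, so provisions in it cannot be ruled out.

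On safety, the protocol relies on published reviews and existing local use, not on these patients alone, and neither document states that zero events will be reported as proof of safety. That tempers the concern. It does not rescue the sample-size sentence, which makes its claim for the 10 patients themselves. Finally, a reader could compute exact intervals from reported counts, but only if the denominators are clear.

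**Conclusion.** The point holds in this limited form and should be corrected. Neither document names a result that would count against the primary hypothesis, intervals are not planned, and the sample-size rationale credits 10 patients with more safety information than they hold. With no events, a rate of up to 30.8% (10 patients) or 16.8% (20 patients) remains compatible with the data at the two-sided 95% level; perfect dosing in 10 leaves the true proportion open down to 69.2%.

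These limits are exact binomial results, assuming independent patients with a common risk. The 82% and 60% chances of seeing no event in 10 rest on the assumed 2% and 5% rates. The case for intervals and for a restrained safety conclusion does not depend on those rates. Specific progression thresholds are a trade-off for the sponsor, and their absence alone does not invalidate the pilot.

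**What to change.** 1. **Intervals and denominators.** In the protocol's Proposed Analyses and in the SAP, report drug-related adverse events, verified correct administration, correct use of study instruments and the completion proportion, each with an exact 95% confidence interval. State the denominators:
   - Safety: all dosed patients. The dose precedes surgery, so this includes any dosed patient later replaced because no stent was placed.
   - Administration: all enrolled and scheduled for dosing, counting as failures those withdrawn for not receiving the drug.
   - Instruments: define correct use and name the denominator, since neither document does.
2. **Sample-size wording.** Replace the claim that 10 patients allow evaluation of serious side effects with the precision available (upper limit 30.8% for 0 of 10, 16.8% for 0 of 20). Report safety as the number of related serious events with its exact upper limit, in place of a conclusion that the regimen is safe.
3. **Optional progression bands.** Pre-specify go, modify and stop bands for moving to the randomized trial on the three primary endpoints, with values chosen and justified by the sponsor. Do not use 10 of 20 completing as a pass mark, given its 41% failure rate at the plan's own implied 50%.

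Items 1 and 2 cost a few sentences and no extra patients. The downside is that the safety and feasibility statements will read less favourably. Item 3 also commits the sponsor in advance to values it may miss.
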